### 3.6 Supplementary study parameters

The following baseline parameters will be collected from patients in the study: age, sex, body mass index, CHA2DS2-VASc score, AF history and duration, details of previous ablation procedures, history of heart disease and previous treatment of heart disease and other related conditions as diabetes, hypertension, thyroid dysfunction, cardiovascular risk factors, failed and current anti-arrhythmic drugs, left ventricular ejection fraction, LA dimensions and volume index, mitral insufficiency grade (0-4), mitral stenosis grade (0-4), any other structural heart disease, INR values at the day of ablation, ACT levels during ablation, total amount of units of heparin infused, total cholesterol, HDL- and LDL-cholesterol, triglycerides, TSH.

Procedural parameters as procedure duration, fluoroscopy time and dose will be collected as well.

In addition, the result from standard follow-up at 12 months after the procedure including recurrence of atrial fibrillation, ECG, medication and symptoms as well as EHRA score and quality of life assessment (AFEQT) will be analyzed to compare long term outcome.

### 3.7 Strategy for the procedure

According to standard clinical protocol and in accordance with international recommendations, after obtaining venous vascular access, a 10-polar catheter is placed in the coronary sinus and one transseptal puncture is performed. After the placement of a steerable sheath (Agilis™, Abbott, Abbott Park, IL), a multipolar mapping catheter PENTARAY™ or OCTARAY™ (Biosense Webster, Diamond Bar, CA, US) or Advisor™ HD Grid (Abbott, Abbott Park, IL) will be deployed in the LA.

The procedure will subsequently consist of two phases:

#### 1: Mapping and randomization in the study

- A voltage map of the LA during atrial pacing will be created. Patients in AF will be cardioverted first. Reconnected PVs will be re-isolated.
- Then pts will be randomized.

#### 2: Intervention

Control group:

- Programmed atrial stimulation (4 extra stimuli (ES) at 350 ms baseline cycle length (CL), with simultaneous decrement of all four ES down to refractory period). If AFL or AF will not be induced with programmed atrial stimulation, then burst pacing (5 s bursts with 10 ms decrement between bursts, starting from CL 300 ms down to 180 ms), will be performed. Mean CL of AF will be measured in left and right appendage. If AFL is induced, this is mapped using a combination of activation and entrainment mapping, but will not be ablated. Patients will be cardioverted to sinus rhythm and no additional ablation will be performed.

Intervention group:

- CTI block and VOM ethanol injection will be performed. Mitral isthmus block will be completed with endocardial and, if necessary, epicardial ablation in coronary sinus followed by dome line. Order of the ablation lines will be performed at the discretion of the physician. Programmed atrial stimulation will be performed as described above, and if AFL or AF will not be induced, then burst pacing will be performed as described above. In case of AF, mean CL will be measured in left and right appendage. No additional mapping or ablation of AF will be performed and the patient will be cardioverted. If AFL is induced, this is mapped and ablated using a combination of activation and entrainment mapping. Afterwards, induction will be performed again until AFL is not inducible anymore. If AF will be induced two times in a row, AF will be cardioverted and the procedure ended. The procedure is ended earlier on the discretion of the operator or if induced AFL is judged non-clinical. All the lines will be checked at the end of procedure for bidirectional block according to the respective institution's standard and a waiting time after the last ablation at a line will be 30 minutes.

### 3.10 Follow up

After 3 months, a clinical follow-up is performed including ECG. If persistent AF or AFL is present, the patient will be cardioverted. AAD (class I and III) will be discontinued at 3 months of follow-up if the patient is in sinus rhythm and discouraged during follow-up. In case of recurrences during follow-up, AAD will be initiated at the discretion of the physician.

In the case of recurrent symptomatic atrial arrhythmia, the patient will be offered a new procedure. However, repeat procedures during the first twelve months will be avoided. In case that a re-procedure cannot be avoided, QOL measurements will be taken immediately before the procedure.

After 12 months, a 5 days Holter recording in addition to an ECG and quality of life assessment (AFEQT) is included. The medical history is reviewed to identify documented AF or AFL as indication of recurrence.

After 24 months and 5 years, an ECG and quality of life assessment (AFEQT) is included.

All follow-up will be performed by personnel blinded for the randomization.

### 3.11 Statistics and data analysis plan

All analysis will be conducted according to the intention-to-treat (ITT) principle (as a superiority analysis) and difference in the primary endpoint AFECT score from baseline to 12 months follow-up will be analysed using student t-test and presented with mean difference and 95% CI.

For secondary endpoints, continuous variables will be evaluated by independent sample student's t-test, discrete variables will be evaluated by Chi-square statistics (or fisher's exact test if applicable), time dependent endpoints will be displayed with Kaplan-Maier curves and compared using a two-sided log-rank test.

Demographic and baseline data will be compared between the two groups. Variables will be expressed as mean  $\pm$  SD, and percentage. If differences exist between groups in baseline data, these variables will be used in final comparison between the two treatment groups as potential confounders.

Procedure related parameters (fluoroscopy-, procedure- and ablation times) will be compared between the two groups and expressed as mean  $\pm$  SD, and percentage.

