### 3.4 Power calculation

Assuming a 10-point difference in the change in AFEQT score between the intervention and control group with 90% power and a 5% significance level, assuming a standard deviation of 20 points (typical standard deviation for QoL in studies using the AFEQT questionnaire), a sample size of 168 patients will be required. With expected dropout during follow-up, 180 patients will be randomized in the study. The study will also be powered for the secondary endpoint (90% power and a 5% significance level, assuming 75% freedom of persistent atrial arrhythmia in the intervention group and 50% in the control group, a sample size of 148 patients is required).

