### 3.5 Study endpoints

Primary endpoint:

- Change in AFEQT score between baseline and 12 months.

Secondary endpoints:

- Freedom from documented atrial arrhythmia at a whole standard ECG recording (regardless of the estimated duration) or Holter/CIED ( $\geq 24$  hours) at 12 and 24 months and 5 years (after 3 months blanking period), on or off antiarrhythmic drugs (AAD).
- Freedom from documented persistent atrial arrhythmia at 12 and 24 months and 5 years (after 3 months blanking period), on or off AAD.
- Freedom from DC cardioverted atrial arrhythmia at 12 and 24 months and 5 years (after 3 months blanking period), on or off AAD.
- Number of DC-cardioversions (after 3 months blanking period) and sustained atrial arrhythmia episodes at 12 and 24 months and 5 years.
- Freedom from accepted chronic atrial fibrillation at 12 and 24 months and 5 years.
- Freedom from re-ablation procedure at 12 and 24 months and 5 years.
- Change in AFEQT score between baseline and 24 months and between baseline and 5 years.

Primary safety endpoints:

- Peri- or postprocedural complications (vascular complication needing intervention, conduction disturbances requiring a pacemaker, gastroesophageal fistula, phrenic nerve damage, stroke or systemic embolism, PV stenosis, cardiac tamponade, anaphylactic reaction, pericarditis and death).

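### Prespecify ANCOVA on baseline AFEQT as the single primary analysis, replacing the unadjusted t-test on change with adjustment triggered by observed baseline differences

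*Protocol*

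**What the plan says.** The primary endpoint in Protocol section 3.5 is "Change in AFEQT score between baseline and 12 months". For its analysis, section 3.11 says that the "difference in the primary endpoint AFECT score from baseline to 12 months follow-up will be analysed using student t-test", reported as a mean difference with 95% CI. No covariate is named. A later paragraph of the same section adds: "If differences exist between groups in baseline data, these variables will be used in final comparison between the two treatment groups as potential confounders". It sets no threshold and gives neither a list of variables nor a model. It also does not say whether the t-test or the adjusted comparison is primary.

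The power calculation (section 3.4) targets 90% power at the 5% level for a gap of 10 points between the arms in AFEQT change. The SD enters there as follows: "assuming a standard deviation of 20 points (typical standard deviation for QoL in studies using the AFEQT questionnaire". On this basis the protocol arrives at 168 patients. The effect is a difference in change, but the SD is described as typical of quality of life in general.

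**The concern.** In a randomized trial, baseline differences between arms arise by chance. The reason to adjust for a covariate is that it predicts the outcome, not that it happens to be imbalanced. Baseline AFEQT is the covariate most directly tied to this endpoint and has to be collected for it, yet section 3.11 would use it only if an undefined imbalance appears.

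Two things follow. The trial gives up precision that costs nothing to obtain. And the protocol leaves two candidate primary results, with the observed baseline data deciding whether the second one exists.

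A smaller point concerns the SD of 20. If it describes the score rather than the change, the power of the planned t-test depends on a correlation that the protocol does not give.

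**Working it through.** **Inputs.** From section 3.4: effect 10 points, SD 20, 90% power, 5% significance level (taken as two-sided), 168 patients, so n = 84 per arm at 1:1. Assumed, because the protocol does not give them: the correlation ρ between baseline and 12-month AFEQT, and the ratio of the two SDs (taken as 1 unless stated). Power is from the noncentral t distribution.

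**1. The plan's own figure.** Using 20 directly as the SD of the analysed variable, the normal approximation gives 85 per arm, or 170 in total, which agrees with 168 to within 2 patients. At 84 per arm the t-test has 89.6% power. The stated size therefore holds if 20 is the SD of the change.

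**2. Why ANCOVA cannot do worse.** Let s0 and s1 be the baseline and 12-month SDs.
- Variance of change: s0² + s1² − 2ρ·s0·s1
- ANCOVA residual variance: s1²(1 − ρ²)
- Difference: (s0 − ρ·s1)², which is never negative

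Apart from one degree of freedom, ANCOVA is at least as precise for any ρ and any SDs.

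**3. If 20 is the SD of change** (equal SDs), the ANCOVA residual SD is 20·√((1+ρ)/2).

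| ρ | ANCOVA SD | ANCOVA power | t-test power |
|---|---|---|---|
| 0.3 | 16.12 | 97.9% | 89.6% |
| 0.4 | 16.73 | 97.1% | 89.6% |
| 0.5 | 17.32 | 96.1% | 89.6% |
| 0.6 | 17.89 | 95.0% | 89.6% |
| 0.7 | 18.44 | 93.8% | 89.6% |

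The 95% CI half-width is 6.09 points for the t-test. For ANCOVA it is 4.91, 5.28 and 5.62 at ρ = 0.3, 0.5 and 0.7. If the 12-month SD is 0.8 times the baseline SD, ANCOVA power over this range of ρ is 99.5% down to 98.2%. At 1.2 times, it is 95.8% down to 90.6%.

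**4. The conditional rule.** The protocol gives no threshold, so the rule was read as adjusting for baseline AFEQT when its baseline comparison has p < 0.05. That happens in 5% of trials. With 100,000 simulated trials per ρ and 20 as the SD of change:

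| ρ | t-test | Rule | ANCOVA | Type I error of rule |
|---|---|---|---|---|
| 0.3 | 89.8% | 91.1% | 97.8% | 4.1% |
| 0.5 | 89.8% | 90.7% | 96.1% | 4.2% |
| 0.7 | 89.7% | 90.1% | 93.5% | 4.6% |

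By subtraction, the rule gains 1.3, 0.9 and 0.4 percentage points, where 8.0, 6.3 and 3.8 are available. Followed mechanically, it does not inflate type I error. If instead the more favourable of the unadjusted and adjusted results could be reported, simulated type I error is 6.7% to 7.8% over the same range (20,000 null trials per ρ).

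**5. If 20 is the SD of the score** (equal SDs), the SD of change is 20·√(2(1−ρ)) and the ANCOVA residual SD is 20·√(1−ρ²).

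| ρ | SD of change | t-test power | ANCOVA power |
|---|---|---|---|
| 0.2 | 25.30 | 72.1% | 90.8% |
| 0.3 | 23.66 | 77.7% | 92.2% |
| 0.4 | 21.91 | 83.7% | 94.0% |
| 0.5 | 20.00 | 89.6% | 96.1% |
| 0.6 | 17.89 | 95.0% | 98.1% |
| 0.7 | 15.49 | 98.6% | 99.5% |

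The SD of change equals 20 at ρ = 0.5. With a 12-month SD of 16 this break-even moves to 0.4 (400 + 256 − 640ρ = 400). With 24 it moves to 0.6 (400 + 576 − 960ρ = 400). With a 12-month SD of 24 and ρ = 0.3, the SD of change is √688 = 26.23 and the t-test has 69.0% power. The ANCOVA SD is then 22.89, with 80.4% power. ANCOVA therefore does not guarantee 90%.

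**The case against.** The t-test on change is a valid test, and it matches the power calculation. Section 3.4 powers a difference in change, and 168 is recovered only when 20 is used directly as the SD of the analysed variable, so the SD of change is the natural reading. On that reading there is no shortfall, and the size of the gain from ANCOVA rests on a correlation that no document gives. The simulated rule is one reading of a vague sentence, and it shows no inflation of type I error. Section 7.6 requires the final analyses to be done blinded to allocation, which limits choosing a model to favour one arm. Thresholds and covariate lists are often left to a statistical analysis plan.

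Much of this stands. The t-test is not invalid, the sample size is not shown to be wrong, and the SD point is a request for clarification. The missing mention of AFEQT in the section 3.6 list ("The following baseline parameters will be collected from patients in the study: age, sex, body mass index" and so on) is not a defect of substance, because the endpoint in section 3.5 already requires a baseline score.

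The core remains. Section 3.11 itself fixes both the unadjusted test and the conditional adjustment, so this is not detail deferred to another document. Blinding hides the arm labels but does not say which result is primary. The precision gain is assured in direction whatever the correlation; only its size is assumed.

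**Conclusion.** The concern holds as a change that should be made, not as a fatal flaw. Section 3.11 makes adjustment depend on chance imbalance and leaves the primary result undefined, while the strongest available covariate goes unused. With 20 as the SD of change and equal SDs at both visits, prespecified ANCOVA raises power at 84 per arm by about 4 to 8 percentage points for correlations of 0.7 down to 0.3, and the conditional rule captures little of that. If 20 is instead the SD of the score, the planned t-test falls short of 90% when the correlation is below 0.5 (with equal SDs). The protocol's wording does not exclude that reading. The correlation, the SD ratio and the 5% trigger are assumptions of this check.

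**What to change.** - **Section 3.11:** prespecify ANCOVA of 12-month AFEQT (or its change) on treatment arm with baseline AFEQT as covariate. Report the adjusted mean difference with 95% CI, and name this the single primary analysis. Delete the adjustment triggered by observed baseline differences. Use the same model for the AFEQT changes to 24 months and 5 years.
- **Section 3.4 (power calculation):** state whether the SD of 20 is that of the score or of the change, give the assumed correlation and 12-month SD, and restate power for the chosen analysis. Do not claim 90% power for every correlation.
- **Section 3.6:** for tidiness, list baseline AFEQT with the other baseline parameters.

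The cost is a few sentences, plus a sourced correlation and 12-month SD for the restated power. No added patients, visits or measurements are needed.

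### Separate t-tests on AFEQT change at 12 months, 24 months and 5 years use, unless missing scores are filled in, only patients with both scores, and ignore earlier scores of patients lost later

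*Protocol*

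**What the plan says.** Protocol section 3.11 opens with the general rule "All analysis will be conducted according to the intention-to-treat (ITT) principle (as a superiority analysis". It then names the primary method in these words: "AFECT score from baseline to 12 months follow-up will be analysed using student t-test and presented with mean difference and 95% CI". The rule it sets for the secondary endpoints is of the same kind: "continuous variables will be evaluated by independent sample student's t-test".

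Section 3.5 gives the primary endpoint as "Change in AFEQT score between baseline and 12 months" and lists among the secondary endpoints "Change in AFEQT score between baseline and 24 months and between baseline and 5 years". The t-test is therefore the fixed method at all three times.

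Section 3.4 (Power calculation) requires 168 patients and adds: "With expected dropout during follow-up, 180 patients will be randomized in the study". It states no dropout rate.

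Section 3.10 schedules AFEQT at 12 months, 24 months and 5 years. The 3-month visit has a clinical check and ECG but no AFEQT. An extra quality-of-life measurement is taken only if a repeat procedure cannot be avoided in the first year. The Protocol overview describes the 60-month follow-up as made through patient files.

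**The concern.** A change score needs two values, and a t-test cannot use a patient who lacks one. Run as written, each test is a comparison of completers, while the section describes all analyses as ITT and the sample size allows for losses. Inflating the sample restores power; it does not bring lost patients into the comparison.

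The weakness is greatest at the later visits. A patient seen at 12 months and lost before 5 years has a 12-month score that helps to predict the missing one. Separate t-tests ignore it. If patients with a poor earlier result leave more often, and the trial's hypothesis holds, more control patients leave. The remaining control patients then look better than the whole arm, and the treatment difference is understated.

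**Working it through.** **1. The plan's own figure.** Inputs from section 3.4: difference 10, SD 20, power 90%, 5% significance (taken as two-sided), 1:1 allocation.

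n per arm = 2 × (1.960 + 1.282)² × 20² / 10² ≈ 84.06, so about 168 in total. The stated 168 reproduces (170 if each arm is rounded up). The allowance for dropout is 180 − 168 = 12, or 12/180 = 6.7%. Power is 91.8% with 180 analysed and 90.0% with 168, so the planned loss does not cost the stated power.

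**2. Bias of the completers' comparison at 12 months.** Let m_I and m_C be the missing fractions in the intervention and control arms, and g the number of points by which the missing patients' mean change is worse than the completers'.

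Bias in the difference = (m_I − m_C) × g, with 90 patients per arm.

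For 12 losses and g = 10 to 20 (assumed), with the larger number lost from control:

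| Losses, control/intervention | g = 10 | g = 20 |
|---|---|---|
| 6/6 | 0 | 0 |
| 7/5 | −2/90 × 10 = −0.2 | −2/90 × 20 = −0.4 |
| 8/4 | −4/90 × 10 = −0.4 | −4/90 × 20 = −0.9 |
| 12/0 | −12/90 × 10 = −1.3 | −12/90 × 20 = −2.7 |

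The last row is an extreme case. Modest imbalance gives 0.2 to 0.9 points against an assumed effect of 10.

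**3. Bias at 5 years.** Assumptions, none of them from the Protocol: true difference 10 at both times, SD of change 20 at both times, correlation 0.6 between the 12-month and 5-year changes, 90 per arm, and a probability of loss that is logistic in the 12-month change and tuned to the loss rates below. The likelihood estimate regresses the 5-year change on the 12-month change within each arm and evaluates it at the mean of all patients with a 12-month score.

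| Loss, control/intervention | t-test, mean estimate | Likelihood, mean estimate |
|---|---|---|
| 31% / 23% | about 9.2 | about 10.0 |
| 28% / 23% | about 9.8 | about 10.0 |

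Repeat runs differ by about 0.1. The size can be checked by hand: with equal SDs, the bias at 5 years is the correlation times the differential selection on the 12-month change. A bias of −0.8 means that selection raises the completers' 12-month mean by 0.8/0.6 ≈ 1.3 points more in control than in intervention. With equal loss unrelated to outcome, both methods average about 10.

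**4. What a model can add at 12 months.** A patient lost before 12 months normally has a baseline score only, so there is almost no further information on the missing value. With assumed loss of about 9% control and 6% intervention that depends on the 12-month outcome, and a baseline correlation of 0.5, the t-test averaged 9.4 to 9.7 and the likelihood estimate 9.6, for a true 10.

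The gain at 12 months is in precision. With equal variances and baseline correlation ρ, the variance of the baseline-adjusted difference relative to that of the difference in raw change is (1 − ρ²) / [2(1 − ρ)] = (1 + ρ)/2. At ρ = 0.5 (assumed) this is 0.75.

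**The case against.** The strongest reply is that section 3.11 nowhere restricts the analysis to patients with both scores. A t-test can follow imputation, and missing-data rules are commonly left to a statistical analysis plan, which may exist. ITT also means analysing patients in the arm to which they were randomised, and a t-test respects that. Allowing for dropout in the sample size is routine and does not define an analysis set. All of this stands. A reader might infer that the Protocol contradicts its own ITT statement or that the primary result is falsely labelled; the text does not support either reading.

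A reader might also infer that many more patients will be lost at 24 months and 5 years. Larger losses over time are plausible, but the Protocol gives no attrition figure.

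It can further be said that a repeated-measures model does little about missing-data bias in the primary endpoint. That is correct, as step 4 shows. A model with baseline as an outcome but no constraint on baseline means would also make the 12-month arm contrast a difference in level, whereas section 3.5 defines change. The fix has to avoid that.

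The objection does not remove the point about the method that is fixed. Three separate t-tests leave scores that the trial already holds unused at the later visits, and a better analysis needs no further data.

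**Conclusion.** The concern holds as a matter of analysis choice. Unless missing scores are filled in, the t-tests in section 3.11 use only patients with both scores, and at 24 months and 5 years they ignore earlier scores of patients lost later.

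Under the assumed 5-year losses and correlation, a true 10-point difference is estimated about 0.2 to 0.8 points too low. That runs toward the null, so a real benefit would be understated; a different pattern of loss could reverse the direction. The likelihood model removes this bias only when loss depends on scores already observed.

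At 12 months the bias is probably small (0.2 to 0.9 points for 7/5 to 8/4 splits), and planned loss leaves power at 90.0%. The stronger reading, that the primary result is seriously biased, needs all 12 losses in one arm, which nothing in the Protocol suggests.

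**What to change.** In section 3.11, replace the separate t-tests on AFEQT change with one likelihood-based repeated-measures model:

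- Outcomes are AFEQT at baseline, 12 months, 24 months and 5 years, for all patients as randomised with any score, with an unstructured covariance.
- Baseline means are constrained to be equal across arms (or baseline is a covariate). The arm contrast at each visit is then the baseline-adjusted difference in change, which keeps the endpoint in section 3.5.
- The 12-month contrast with 95% CI is primary; the 24-month and 5-year contrasts come from the same model.
- One sensitivity analysis shifts unobserved 12-month scores by a fixed amount that may differ by arm. This is what addresses missing data in the primary result.
- The t-test stays as a supportive analysis, labelled complete-case.

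Reconcile the Protocol overview, which describes 60-month follow-up through patient files, with section 3.10, which includes AFEQT at 5 years; the 5-year contrast depends on the answer.

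The cost is a few sentences, slightly more analysis work and a less simple primary method. No new patients or visits are needed.

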### 3.2 Study design

This study is a prospective, patient and assessor blinded, 1:1 randomized superiority trial. Consecutive patients referred for re-ablation of symptomatic PsAF after previous PVI will be included. All preoperative procedures will be conducted according to the department's standard operational procedures for AF ablation. In all patients, an electro anatomical map (CARTO™, Biosense Webster, Diamond Bar, CA, or EnSite X™, Abbott Laboratories, Abbott Park, IL) of the LA with a multipolar mapping catheter (PENTARAY™ or OCTARAY™, Biosense Webster, Diamond Bar, CA, or Advisor™ HD Grid, Abbott Laboratories, Abbott Park, IL) will be constructed and reconnection of PVs will be assessed in sinus rhythm. If reconnection is present, re-PVI will be performed and confirmed with the multipolar mapping catheter. Patients in atrial fibrillation will undergo cardioversion to sinus rhythm prior to mapping. After mapping and confirming isolation of the PVs, patients will be randomized using the Redcap Database software to intervention or control. The intervention group will undergo VOM ethanol ablation including supplementary LA and coronary sinus ablation, if needed to achieve mitral isthmus block plus creation of dome line and cavotricuspid isthmus (CTI) block according to section 3.7. VOM ablation, mitral and CTI ablation and dome line will not be performed in control group and patients in control group will undergo no further ablation. The energy source used will be radiofrequency ablation or pulsed field ablation, at the discretion of the physician. However, radiofrequency should be preferred near coronary arteries. For dome line, focal PFA is preferred. All post-procedural work-up and follow-up will be the same for both randomization groups and assessment of outcomes will be performed by personnel blinded to randomization.

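### Section 3.11 lets observed baseline imbalance choose the adjustment covariates, and section 3.6 files total heparin and ACT as baseline although randomisation is mid-procedure

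*Protocol*

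**What the plan says.** Section 3.11 opens with the general principle "All analysis will be conducted according to the intention-to-treat (ITT) principle (as a superiority analysis"). It assigns the primary endpoint, AFEQT change from baseline to 12 months, to an unadjusted comparison that "will be analysed using student t-test and presented with mean difference and 95% CI". Two paragraphs later, after saying that demographic and baseline data will be compared between arms, it adds: "If differences exist between groups in baseline data, these variables will be used in final comparison between the two treatment groups as potential confounders". It gives no list of covariates and no criterion for a difference. It does not say whether the adjusted comparison replaces the t-test or stands beside it.

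Section 3.6 introduces its list with "The following baseline parameters will be collected from patients in the study", and that list includes "ACT levels during ablation, total amount of units of heparin infused". A separate sentence follows: "Procedural parameters as procedure duration, fluoroscopy time and dose will be collected as well". Section 3.11 has its own procedural list: "Procedure related parameters (fluoroscopy-, procedure- and ablation times) will be compared between the two groups". Neither procedural list contains heparin or ACT.

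On timing, section 3.2 states: "After mapping and confirming isolation of the PVs, patients will be randomized using the Redcap Database software to intervention or control". Sections 3.7 and 3.12 agree. After randomisation, controls have no further ablation. The intervention arm has the vein of Marshall ethanol injection, the lines and a waiting time, and section 5.1 expects about 60 more minutes for it.

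**The concern.** There are two faults, and they compound.

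1. **Selection by imbalance.** In a randomised trial, differences in variables measured before randomisation are due to chance. Whether a variable happens to differ says nothing about whether it predicts AFEQT. The rule therefore chooses covariates on the wrong criterion, and only after the data are in.
2. **A post-randomisation variable in the baseline list.** Total heparin is a running total over a procedure whose later part differs by arm. It can differ because of treatment. Read literally, the rule then requires it as a confounder. Adjusting for something treatment has changed no longer estimates the total effect of allocation, which is what the intention-to-treat comparison in the same section targets.

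That treatment shifts heparin is an inference, because the protocol gives no anticoagulation timing. It is weaker for ACT, which is a level and not a total.

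**Working it through.** **The plan's own figure.** Inputs from section 3.4 (Power calculation): difference 10, SD 20, 5% significance (two-sided assumed), 90% power.

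- Total N = 4 × (1.960 + 1.282)² × 20² / 10² = 168.1, which matches the stated 168.
- With 84 per arm, SE = 20 × √(2/84) = 3.086, and the t-test has power 89.6%.

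**How often the trigger fires by chance.** The number of variables, their independence and a 5% threshold are assumptions. P(at least one difference) = 1 − 0.95^k, which is 64%, 72% and 79% for k = 20, 25 and 30. Some data-chosen adjustment is more likely than not.

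**Effect of adjusting for a treatment-shifted covariate.** Assume allocation shifts the covariate by d within-arm SDs, and that the covariate has within-arm correlation r with AFEQT change. With equal arms:

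- movement of the estimate = r × 20 × d (down if r is positive, up if r is negative);
- SE factor = √[(1 − r²)(1 + d²/4)];
- power and false-positive rate from the noncentral t with 165 df. The false-positive rate is the rejection rate when allocation has no total effect on AFEQT.

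Example, |r| = 0.2 and d = 0.5: movement = 0.2 × 20 × 0.5 = 2.0 points; SE factor = √(0.96 × 1.0625) = 1.010.

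| \|r\| | d | Movement (points) | SE factor | False-positive rate | Power at true effect 10 |
|---|---|---|---|---|---|
| 0 | 0.5 | 0 | 1.031 | 5% | 87.8% |
| 0 | 1.0 | 0 | 1.118 | 5% | 82.2% |
| 0.1 | 0.5 | 1.0 | 1.026 | 6.1% | 81% (r>0) or 93% (r<0) |
| 0.1 | 1.0 | 2.0 | 1.112 | 8.9% | 64% or 94% |
| 0.2 | 0.3 | 1.2 | 0.991 | 6.8% | 82% or 95% |
| 0.2 | 0.5 | 2.0 | 1.010 | 9.8% | 72% or 97% |
| 0.2 | 1.0 | 4.0 | 1.095 | 21.7% | 42% or 98% |

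The interval does not always widen. At |r| = 0.2 the SE factor is below 1 for d under 2 × √(1/0.96 − 1) = 0.41.

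**With the trigger included.** These are simulations of adjusting only if the covariate differs at p < 0.05 (threshold assumed, 8,000 runs each).

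- d = 0.5: the covariate is selected in about 90% of trials. The mean estimate of a true 10 is 8.1 (r = +0.2) or 11.9 (r = −0.2), and null rejection is 9.4% to 9.7%.
- d = 1.0: it is selected in 100% of trials. The means are 6.0 and 14.0, and null rejection is 21.0% to 21.8%.
- r = 0: the means are 9.95 and 10.00, and null rejection is 5.0% and 4.8%.

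The trigger gives almost no protection, because a shift of this size is what it detects.

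**The case against.** The strongest reply is that the primary analysis is already named: an unadjusted t-test, which cannot carry covariates. The imbalance sentence sits in the paragraph on demographic data and mentions neither AFEQT nor the primary endpoint. On that reading the adjusted comparison is a sensitivity analysis and the primary result is untouched. That is fair, but the protocol calls the adjusted analysis the final comparison and never ranks the two.

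Second, the rule does no demonstrable damage through true baseline variables. A simulation with 20 independent variables and one prognostic variable (correlation 0, 0.3 or 0.5; 4,000 runs each) gave null rejection of 4.8%, 4.9% and 3.5%, with the mean null estimate within 0.1 point of zero. This stands: that half is a fault of practice, not a source of bias.

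Third, the heparin harm needs a chain of conditions: that section 3.11's baseline data means the section 3.6 list, that heparin differs by arm, that it correlates with AFEQT change within arms, and that the adjusted result prevails. The protocol gives no evidence for the correlation. At |r| = 0.05 the false-positive rate is only 5.3% (d = 0.5) or 6.0% (d = 1.0). This also stands, and it limits what can be said about size.

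Blinded final analysis (section 7.6) limits favourable picking. It does not keep a treatment-driven variable out of a rule that is worded as mandatory.

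**Conclusion.** The concern holds and should be fixed. The textual defect is certain: the protocol itself states the selection rule and the classification, so an analysis plan that followed it would inherit both. The harm is conditional. It reaches the main result only if the adjusted comparison is the final one, and biases it only if treatment shifts the chosen variable and that variable correlates with AFEQT change within arms. Over the assumed range (shift 0.5 to 1.0 SD, |r| from 0 to 0.2) the consequence runs from no bias with a modest loss of power to a 4.0-point movement in either direction, against a design difference of 10. None of these shifts or correlations comes from the protocol. Confidence is medium for that reason.

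**What to change.** - **Section 3.11:** delete the imbalance-triggered sentence. State that the primary analysis compares 12-month AFEQT change between arms, adjusted for baseline AFEQT whatever the observed balance, and reports the mean difference with 95% CI. Label any other adjusted analysis supplementary. Add that no variable measured wholly or partly after randomisation is used as a covariate.
- **Section 3.6:** move ACT and total heparin to the procedural parameters.

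Deleting the trigger and moving the two items removes the defect. The baseline AFEQT adjustment is a separate efficiency gain that replaces the trigger.

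The cost is wording only. The endpoint already requires baseline AFEQT, N stays at 168/180, and one degree of freedom is used. The gain depends on the baseline-to-12-month correlation ρ (assumed, with equal variances) and on whether the SD of 20 refers to the change or to the score, which section 3.4 (Power calculation) leaves open.

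| ρ | 20 is SD of change: unadjusted → adjusted power | 20 is SD of score: unadjusted → adjusted power |
|---|---|---|
| 0.3 | 89.6% → 97.9% | 77.7% → 92.2% |
| 0.5 | 89.6% → 96.1% | 89.6% → 96.1% |
| 0.7 | 89.6% → 93.8% | 98.6% → 99.5% |

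In the first case the variance of the change is multiplied by (1 + ρ)/2. In the second, the SD of the change is 20√(2(1 − ρ)) and the residual SD after adjustment is 20√(1 − ρ²). Power rises in every case.
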